1.1 Background

Central nervous system disorders are currently being symptomatically treated since the molecular events provoking their onset have not been yet identified. Drug delivery techniques have to overcome the almost impermeable blood-brain barrier (BBB) and can be grouped into two main categories: (i) invasive and targeted, and (ii) non-invasive and non-targeted methods. However, the technological advances of the past decades revealed the immense potential of focused ultrasound (FUS) in transcranial applications. In contrast to other techniques, FUS-mediated BBB opening is both non-invasive and targeted. The localized energy delivery coupled with the circulation of intravenously administered microbubbles initiates biological effects confined only to the vessel walls and contained only in the targeted region within the brain.

Microbubbles are gas-core, lipid-shelled particles with diameters between 1-10 μ m. Their minute size allows them to circulate throughout the vasculature. Microbubbles are compressible, thus they respond to the alternating phases of an ultrasound wave by expanding and contracting. These volumetric oscillations exert stresses onto the surrounding vascular walls and temporarily open the tight junctions that formulate the BBB. The magnitude and distribution of this bioeffect can be controlled by adjusting the sonication parameters. BBB opening using FUS and microbubbles is fully non-invasive and has been proven to be safe and reversible. The integrity of the BBB is being restored within hours depending on the selected parameters. This technique has shown efficacy in delivering various compounds in the brain parenchyma such as contrast agents, sugars, antibodies, viruses, chemotherapeutics and neurotrophic factors in both benign and diseased brains. In the context of Alzheimer's disease (AD), FUS has been shown to effectively decrease amyloid plaque load in AD rodents. Moreover, rodents tested behaviorally showed significant memory improvement following FUS treatment [1-13].

1.2 Investigational Device

Device name: Focused Ultrasound by Sonic Concepts

Device description: A single-element, spherical-segment FUS transducer (H-231, Sonic Concepts, Bothell, WA) driven by a function generator (Agilent, Palo Alto, CA, USA) through a 50-dB power amplifier (E&I,

Page 2

Rochester, NY, USA). The confocally mounted hydrophone (Y107, Sonic Concepts, WA, USA) is driven by a preamplifier (Olympus, Waltham, MA, USA). **Device Model/Version #:** H-231

Device name: Neuronavigation System by Rogue Research **Device description:** This device will be used for monitoring the procedure. **Device Model/Version #:** Brainsight system 2.3.3

Drug name: Definity Dose: 10 μl/kg Route of administration: Intravenous This drug is FDA-approved (NDA 21-064) but not being used in accordance with labeling.

Drug name: Dotarem Dose: 0.2 ml/kg Route of administration: Intravenous This drug is FDA-approved (NDA 20-4781) but not being used in accordance with labeling.

Drug name: Florbetapir F¹⁸ **Dose:** 370 MBq (10 mCi) – 10 ml bolus injection **Route of administration:** Intravenous This drug is FDA-approved (NDA 20-2008) and used in accordance with labeling.

Device name: Vantage

Device description: A programmable ultrasound research platform used for performing specialized and customizable ultrasound scans. (Verasonics, Inc, Kirkland, WA) will be connected to an array transducer (ATL Phillips, WA, USA) to achieve real-time passive acoustic monitoring. **Device Model/Version #:** Verasonics Vantage 256

1.3 Preclinical Data

FUS has been extensively studied in safely opening the BBB of various animal species and different disease-mimicking models. The application of FUS in conjunction with pre-formed intravenously administered microbubbles produces bioeffects which are confined only within the targeted region. Our group and others have shown that this targeted drug delivery system can be successfully applied in preclinical studies on rodents, rabbits, pigs, and non-human primates (NHP). This technique has shown efficacy in delivering a wide range of drugs into the brain. Furthermore, FUS-mediated BBB opening has been shown to effectively decrease the amyloid plaque load and restore memory in AD rodents, even without the administration of an anti-AD drug [1-13].

Our group has published extensive work confirming the accuracy and safety of this technique performed both in rodents and, more recently, in NHP. We have shown that the BBB can be safely and reversibly opened using focused ultrasound and microbubbles, and that its integrity is restored within 2 days in rodents and between 2 and 4 days in NHPs. Recently, our group focused on developing a new clinical system. The new system consists of two parts: (i) ultrasound unit for sonication, real-time passive acoustic monitoring, and B-mode imaging and (ii) neuronavigator providing real-time guidance. In contrast to MR-guided FUS which requires sonication within an MRI magnet, our approach is based on an open-space, neuronavigatorcontrolled sonication. The real-time guidance is achieved by registration of the physical space to the preloaded MRI that is displayed on the screen. The registration is achieved by the infrared camera reflecting the position of the beads secured close to the brain. The transducer is attached on the neuronavigator arm and the position varies depending on the structure that will be sonicated. The transducer carries beads as

well so its relative position to the brain can be seen on the screen. Once the transducer is locked at the position of interest, the sonication starts. Real-time monitoring of the sonication by passive cavitation detection or passive acoustic mapping can be used to address the efficacy and safety of the technique. B-mode ultrasound imaging is also performed to acquire anatomical information. In B-mode imaging, a short pulse (<5 cycles) will be used and the mechanical index (MI) will be maintained below 0.1, well below the FDA limit of 1.9 MI. The sonication procedure coupled with the neuronavigation system has been tested on sitting, awake primates and the resulting BBB opening was similar to the results obtained from our previous equipment [14-20].

1.4 Clinical Data to Date

There are a few completed clinical studies while some are in progress. In France, researchers have implanted a transducer through the patients' skull and at each session they sonicate at low intensity to achieve a BBB opening to assist glioblastoma multiforme (GBM) chemotherapeutic treatment. The results have shown successful BBB opening along the ultrasound beam path and targeted drug delivery within the brain tumor and its adjacent tissue. However, this approach is restricted by invasive surgery resulting in the lack of flexibility and selection of the targeted area. Our study aims to overcome this limitation through neuronavigation guidance and using a noninvasive single-element transducer. In Canada, researchers have treated patients for the same purpose, i.e. BBB opening for chemotherapeutic drug delivery in GBM, without implanting the transducer but instead sonicating through the intact skull with MR guidance. Another trial from the Lipsman et al. focused on opening the BBB in patients diagnosed with early AD using the same MR guided ultrasound system. Published results from these trials have confirmed that a reversible BBB opening in humans is both feasible and safe.

1.5 Research Risks & Benefits

1.5.1 Risk of Investigational Device

Ultrasound and MRI are generally considered safe imaging modalities. However, there are potential risks related to their usage.

Although ultrasound exposure at high intensities may produce unintended biological effects in the body, such as hemorrhage and edema, our study will be limited to intensities far below the FDA-approved limits for imaging applications ($I_{SPPA} < 190 \text{ W/cm}^2$, $I_{SPTA} < 720 \text{ mW/cm}^2$ and MI < 0.8). FUS is expected to induce some intended mechanical effects in the brain, but there has been no damage reported in the literature during low-intensity sonication. Sonications at relatively high acoustic pressures have resulted in moderate hemorrhage at the targeted region, leading to instances of edema and inflammatory response. We will therefore operate close to the threshold for stimulation to avoid any unwanted effects and minimize the risk for the patient. It is possible that the patient will feel some heat from the ultrasound propagation through the skull. We will account for potential heating by using a cooling medium (i.e., cold water) between the transducer and the skull. All the necessary hardware and software precautions will be taken, in order to eliminate the possibility of transducer malfunction or protocol breach during the clinical sessions. For ultrasound B-mode imaging, the mechanical index (MI) will be maintained below 0.1, well below the FDA limit and there will be no heating or feeling by imaging.

Definity microbubbles are FDA-approved (NDA 21-064) and are routinely used in ultrasound imaging applications, such as echocardiography or renal imaging, for over 15 years. There have been reported side effects such as cardiopulmonary reactions, injection site reaction, back/renal pain, chest pain, dizziness, headache, nausea etc. Other possible risks during the procedure include bruising at the injection site, and hypersensitivity or allergic reaction to Definity microbubbles and/or gadolinium injections. All the potential

adverse reactions and their incidence rate can be found in the Definity and gadolinium safety datasheets which are attached to our protocol. In our study, we will use the clinically recommended dose of 10 μ l/kg introduced by intravenous bolus injection followed by a 10 ml saline flush, according to the manufacturer's guidelines. Over the course of the study, the bolus injection may be replaced by a syringe-pump-controlled infusion within 30-60 seconds. We have shown that FUS treatment using the clinically recommended dose of Definity and the minimum ultrasound parameters (MI: 0.4) can safely open the BBB with 100% success rate, without compromising safety (appendix 6.1). We have also proved that the BBB is completely restored within 3 days after FUS treatment.

In the MRI the patient may experience anxiety or claustrophobia because of the small space he/she will have to spend an hour. However, this can be accounted for with proper preparation of the patient and/or providing music during the acquisition. Also, the strong electromagnetic fields used in MRI pose an underlying risk for patients. Therefore, any patients bearing metallic implants or pacemakers will be excluded from our study. PET tracer Amyvid (¹⁸F- Florbetapir) may also cause allergic reactions to patients.

1.5.2 Other Risks of Study Participation

Other possible risks during the procedure include bruising at the injection site.

1.5.3 Potential benefits

Subjects participating in research may not benefit directly from this study due to the absence of anti-AD drugs. There is evidence that BBB opening through FUS application removes amyloid- β plaques and restores memory in an AD mouse models, even without drug administration [13]. However, there is no data on plaque reduction in a NHP model. Nevertheless, the information collected from this study may help others in the future by establishing that this technique is safe and efficient in achieving reversible BBB opening. Feasibility of small BBB openings in the brain with safety confirmed on MRI will open avenues for future clinical trials with potent drugs that are currently shelved due to their BBB impermeability.

2 Study Objectives

2.1 Primary Objective

The purpose of this study is to assess the safety and feasibility of FUS-induced BBB opening in human subjects using a single-element transducer with neuronavigation guidance. We have built and tested a new system for clinical application, based on the system used in our NHP studies. The human module for the neuronavigator will be implemented and initial safety in a small cohort of patients with early AD will be tested. Given the promising results obtained in *ex vivo* human skulls and the safety profile established in NHP *in vivo* over the past five years, our primary objective is to demonstrate initial clinical feasibility in patients with AD.

In the clinical neurological practice, it is well known that over the past decade there has been a lull in the treatment of the disease without any of the pharmacological agents capable of slowing down the disease. Invasive alternatives such as deep brain stimulation (DBS) are currently in clinical trials. In this aim, initial feasibility and safety of the noninvasive FUS technique on patients *in vivo* will be performed. The information collected in this study may be used to design future clinical trials – to ultimately provide a viable alternative for treatment of AD in a safe and noninvasive manner.

2.2 Secondary Objective(s)

A secondary objective is to define the minimum ultrasound parameters required to safely and reversibly open the BBB in humans. These parameters will provide the threshold of FUS-induced BBB opening and will be used in future clinical studies aiming at targeted brain drug delivery using FUS. Based on our animal study report (appendix 6.1), treatment at MI of 0.4 produced BBB opening in all subjects. Therefore, the objective here is to define the success rate using these minimum parameters which are close to the BBB opening threshold.

3 Study Design

3.1 General Design

The clinical neuronavigator will be identical to the NHP study with the difference of human module (Brainsight) in the software used, as well as employing a separate set of navigation tools that are used for human subjects only. Similar to the NHP study, initial feasibility of the system targeting will be shown with the channel phantom using ex vivo human (parietal bone) skulls as in our preliminary studies.

The neurologist on the study, [name], MD at the Taub Institute of Alzheimer's Disease and Aging at Columbia, will be guiding this clinical application. The subjects will first be diagnosed at Columbia. Six (6) patients will be asked to participate in this initial safety and feasibility study. The subjects will have to meet at least the following criteria: 1) 50 years old or older, 2) have been diagnosed with early AD or mild cognitive impairment (MCI) at minimum and 3) ability to provide informed consent. Approvals and consent forms approved by the Clinical Trials Office (CTO) and the Institutional Review Board (IRB) of Columbia University will be obtained through an IRB approved study (CTO will guide the pre-IDE approval in the first year). All subjects agreeing to participate will undergo the following series of procedures: 1) a high-resolution MRI (without gadolinium contrast agent) will be acquired prior to BBB opening on the GE SIGNATM Premier (3T) (same scanner as in the NHP study) for pre-treatment planning and screening purposes. Also, a PET/CT scan with Amyvid (18F-Florbetapir) will be performed on the SIEMENS Biograph 64 to assess the baseline amyloid plaque load before the treatment. 2) BBB opening will be attempted (in a designated facility in Radiology) using the clinical FUS system. First, a baseline signal will be acquired by applying ultrasound prior to microbubble injection. Then, an intravenous injection of Definity microbubbles under the FDA guidelines will be administered as a bolus or via a syringe pump and cavitation signal will be monitored and recorded during sonication at parameters under the FDA safety guidelines. 3) A MRI (with and without gadolinium) will be acquired immediately after the sonication in order to assess the BBB opening and safety. 4) A follow-up MRI (with and without gadolinium) will be conducted 3 days (±1 day) after the treatment to confirm BBB closing and/or safety. Also, two follow-up PET/CT scans using Amyvid (¹⁸F-Florbetapir) will be conducted 3 weeks (±1 week) and 3 months (± 2 weeks) post-FUS to assess amyloid plaque load.

MRI will be performed at the Neurological Institute of New York / CUMC.

3.2 Primary Study Endpoints

Feasibility of FUS-induced BBB opening in humans.

3.3 Secondary Study Endpoints

Optimization of FUS parameters for future studies.

3.4 Primary Safety Endpoints

Safety of the technique will be assessed by MRI and neurocognitive tests, to guarantee that FUS-induced BBB opening at low frequency and pressure does not cause adverse effects in patients.

4 Subject Selection and Withdrawal

4.1 Inclusion Criteria

AD patients will be recruited in person and have to be over 50 years of age and able to give consent. Patients diagnosed with early stages of AD or with MCI will be included in our study. Other more severe symptomatic patients will be eligible to enroll, as long as they have the ability to consent for their participation. Screening is essential and will be performed by our collaborator and neurologist of the study, [name], MD at the Taub Institute of Alzheimer's Disease and Aging at Columbia. After the initial screening we will acquire MRI scans as part of the study and finalize enrollment or exclusion of the patient. Inclusion criteria thus include:

- Age greater than 50 years old.
- Diagnosis of early AD or MCI at minimum. All following criteria must be met:
 - Probable MCI or AD consistent with criteria outlined in (McKhann *et al* 2011, Petersen *et al* 2018).
 - MMSE score between 12 and 26.
 - Modified Hachinski Ischemia Scale (MHIS) score of <= 4
 - Short form Geriatric Depression Scale (GDS) score of ≤ 6 .
 - PET scan confirming amyloid plaque load using Amyvid (¹⁸F-Florbetapir).
- Ability to provide informed consent.

4.2 Exclusion Criteria

Exclusion criteria include surgeries and other pathologies not associated with AD, as outlined in the following list:

- Contraindication for MRI.
- Contra-indication history or hypersensitivity to MRI contrast agents (e.g., Dotarem) or microbubbles (e.g., Definity).
- Prior brain surgery, including deep brain stimulation.
- Metallic implants.
- Moderate or severe uncontrolled hypertension.
- Abnormal coagulation profile, e.g. hemophilia A or B.
- Coagulopathy or under anticoagulant therapy.
- History of stroke or cardiovascular disease.
- Active gingivitis, herpes simplex, hepatitis, tuberculosis, and minor skin or respiratory infections.
- History of seizure disorder.
- History of asthma or allergies to food or medication with significant symptoms in past 3 years.
- Severe brain atrophy.
- Inability to comply with the procedures of the protocol, including follow-up MRI scans.
- Pregnancy or lactation.
- Impaired renal function with estimated glomerular filtration rate (eGFR) <30 mL/min/1.73m² provided by a standard blood test 2-4 weeks prior to the ultrasound treatment.
- Active infection/inflammation.
- Acute or chronic hemorrhages, i.e. > 4 lobar microbleeds, and no siderosis or macrohemorrhages.
- Tumors or space occupying lesions.
- Meningeal enhancements.
- Intracranial hypotension.

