8.5 Stopping Rules

Redundant safety features have been added to the hardware of the device, as grounding for the transducer, safety switch for the amplifier and function generator. Additionally, we will incorporate safety valves in our software. For any signs showing safety risk including high cavitation dose in the acoustic monitoring or unstable vital signs, the device can be stopped from the computer user interface and/or an emergency stop button. Treatment will be stopped in the case of any reaction of the subject to the ultrasound exposure or microbubble infusion. Pulse oximetry will be used during MRI scans to mitigate the risk of anaphylactic reaction to MRI contrast agents. Potential adverse effects have been grouped according to their severity in the following table:

Severity	Adverse effect			
Severe	Local hemorrhage	Edema	Intracranial infection	Status epilepticus
Moderate	Emesis	Dizziness	Allergic reaction	Nausea
Mild	Skull heating	Injection site bruising	Headache	

The investigation will be paused and the relevant authorities will be notified in case of any death, life threatening event, or any other serious adverse event described in the table above (including disability or clinically significant manifestation of local hemorrhage or edema) due to the procedure. An episode of status epilepticus during treatment will terminate the session immediately.

If the selected ultrasound settings (i.e., MI of 0.4) do not successfully open the BBB in 3 subjects, FDA will be contacted via a submission of an IDE supplement, to discuss revising the protocol's focused ultrasound parameters or increase the number of subjects.

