8.6 Medical Monitoring

Medical monitoring will be performed by the neurologist of this study, [name], MD at the Taub Institute of Alzheimer's Disease and Aging at Columbia. [name] or any other trained radiologist will be present during the trial and will assess the subject's clinical status during therapy. In the case of an allergic or any other reaction (e.g. status epilepticus) to the therapy, the study will be immediately discontinued. Resuscitation equipment will be readily available in the study room, in case of a serious adverse event.

Subjects will be monitored with follow-up MRI scans to confirm BBB opening and closing and PET scans to estimate amyloid plaque load. Should the MRI or PET brain scans of this study have incidental findings (e.g. brain tumor, subarachnoid hemorrhage, or structural abnormality) the subject will be immediately withdrawn from the study and directed for clinical care. MRI scans will be examined by [name], who is a certified in Diagnostic Radiology and is the Section Chief of Neuroradiology. MRI scan examination by [name] will occur as soon as possible but no later than two weeks following receipt of the image.

If there are any incidental findings deemed by the clinical-investigator to be "life-threatening" or "important but not severe", both the subject and the subject's personal primary care physician will be notified. Communication may be initially verbal, followed by a formal written communication. The significance of the incidental finding will be determined by the clinical-investigator and communicated to the subject accordingly. Incidental findings of clinical significance and the management of such findings should be documented in the research records of this study.

At the time of a continuing review, if incidental findings were noted during the previous approval period, the principal investigator of this study will provide the IRB with the following information: the number of required review images, a list of the subject study numbers, the type of scan, the date of the scan, a description of the incidental finding of clinical significance, the date of communication with the subject and the outcome, if known.

If the participants expressed severe depression or suicidal ideation in the course of their visit, the subject will be urgently assessed by the study clinician and appropriate referrals will be made. In addition, we will exclude the participant from the study.

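### The hemorrhage exclusion in Section 4.2 contradicts itself, so the text does not settle whether siderosis, macrohemorrhage or a low microbleed count excludes a patient

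*Combined protocol and SAP*

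**What the plan says.** Section 4.2 opens by fixing the direction of the list: "Exclusion criteria include surgeries and other pathologies not associated with AD, as outlined in the following list". Meeting an item therefore excludes the patient. The hemorrhage item reads "Acute or chronic hemorrhages, i.e. > 4 lobar microbleeds, and no siderosis or macrohemorrhages".

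The item is applied to imaging. Section 4.1 states: "After the initial screening we will acquire MRI scans as part of the study and finalize enrollment or exclusion of the patient".

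Two other provisions touch on bleeding. Section 4.2 also excludes for "History of stroke or cardiovascular disease". Section 8.6 has a rule that begins "Should the MRI or PET brain scans of this study have incidental findings (e.g. brain tumor, subarachnoid hemorrhage, or structural abnormality" and goes on to require immediate withdrawal and referral for care.

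On safety, Section 3.4 says that MRI and neurocognitive tests will be used. The table in Section 8.5 places local hemorrhage in its severe row, and the text below it pauses the investigation for events due to the procedure that include "clinically significant manifestation of local hemorrhage or edema".

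**The concern.** Every other item in Section 4.2 names something whose presence or degree excludes. This item alone carries a clause beginning with *no*, which is the form of an inclusion criterion. An inclusion-style condition seems to have been merged into an exclusion, and the result can be read in ways that give opposite answers for the same patient.

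Two things are at stake. The first is subject protection: this is the only line that names siderosis or macrohemorrhage, and a screener, monitor or auditor cannot tell from it whether a patient who has them is eligible. The second is interpretation: the pause rule in Section 8.5 turns on whether a hemorrhage is due to the procedure, and that judgement is easier when the bleeding status allowed at entry is clearly defined.

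**Working it through.** The plan gives no figure on this point, so the check is one of logic.

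**Inputs.** All come from the hemorrhage item in Section 4.2. Let M mean more than 4 lobar microbleeds, and S mean that siderosis or a macrohemorrhage is present.

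**Readings.**
- A, where *i.e.* defines the excluded state by all that follows it: exclude if M and not S.
- B, where the opening words govern: exclude for any acute or chronic bleed.
- C, the probable intent: exclude if M or S.

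Reading B is worked out on the assumption that a microbleed and siderosis each count as a hemorrhage.

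| Screening MRI | A | B | C |
|---|---|---|---|
| No microbleeds, no S | not excluded | not excluded | not excluded |
| 1 to 4 microbleeds, no S | not excluded | excluded | not excluded |
| More than 4 microbleeds, no S | excluded | excluded | excluded |
| 0 to 4 microbleeds, S present | not excluded | excluded | excluded |
| More than 4 microbleeds, S present | not excluded | excluded | excluded |

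**Results.**
1. Crossing M with S gives four combinations. A and C differ in two of them, namely the two with S present. Under A, a patient with more than 4 microbleeds is excluded, but the same patient with a macrohemorrhage as well is not caught by the item.
2. B and C differ in one row, 1 to 4 microbleeds without S. Under B the threshold of 4 does no work, and the closing clause conflicts with the opening words, because a macrohemorrhage is itself a hemorrhage.
3. All three readings agree in only two of the five rows.

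**Does another section settle it?**
- Stroke history, Section 4.2: this may catch a macrohemorrhage recorded as a stroke. It does not clearly cover a silent one, and it does not name siderosis.
- Coagulopathy and anticoagulant therapy, Section 4.2: these are risk factors for bleeding, not imaging findings.
- Incidental findings, Section 8.6: this is a withdrawal rule, not an eligibility criterion. Its examples include subarachnoid hemorrhage and structural abnormality, but not siderosis, and it sets no microbleed count.
- Sections 3.1, 4.3 and 6: these repeat some inclusion criteria and do not mention hemorrhage.

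Siderosis and macrohemorrhage are named nowhere else in the document, so nothing in it chooses between the readings.

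**The case against.** The strongest reply is that the intent is plain. Reading A is clinically perverse, the item opens with hemorrhage as the excluded condition, and a neurologist screens each patient, with MRI before enrollment is finalized. Such a reader would very probably apply reading C. The stroke, coagulopathy, anticoagulant and incidental-finding provisions narrow the practical exposure further.

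Much of this stands. It defeats the stronger inference a reader might draw, that the criterion is simply inverted and the protocol admits patients with siderosis or macrohemorrhage. That follows from one reading only. The microbleed clause has the right direction for an exclusion list, and the opening words can be read to cover macrohemorrhage. What the reply does not do is make the text determinate: it relies on the screener's guess, and the backstops neither name siderosis nor restate the rule.

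Three further inferences are tempting but unsupported:
- That hemorrhage is the main device risk. Section 1.5.1 names it together with edema, and Section 8.5 puts it in the same row as edema, intracranial infection and status epilepticus. The statement "Sonications at relatively high acoustic pressures have resulted in moderate hemorrhage at the targeted region" concerns pressures that the section says the study will avoid by working close to threshold.
- That a misclassified subject shifts a hemorrhage rate by a known amount among the six planned. The plan defines no hemorrhage-rate endpoint, and Section 3.4 does not mention hemorrhage.
- That an old bleed would be counted as a new one. Every subject has a pre-treatment MRI (Sections 3.1 and 6.1), and Section 5.7 plans a contralateral comparison for safety.

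**Conclusion.** The concern holds as a drafting error in an operative eligibility rule. The hemorrhage item is self-contradictory: under one construction it fails to catch patients with siderosis or macrohemorrhage, and under the other its numerical threshold is redundant. The size is logical, not numerical: the literal definition and the probable intent disagree in two of four combinations, exactly those with siderosis or macrohemorrhage present.

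The conclusion rests on the wording of Section 4.2 and on the absence of a clarifying statement elsewhere in the document. The row for 1 to 4 microbleeds also assumes that a microbleed counts as a hemorrhage under reading B. The documents do not show that anyone was wrongly enrolled, and no effect on a trial result can be calculated from them. The line should be corrected because it governs a safety-related entry decision in a study that assesses safety by MRI and has a pause rule for clinically significant procedural hemorrhage.

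**What to change.** Replace the single item in Section 4.2 with separate exclusion items for acute hemorrhage, lobar microbleed count, siderosis and macrohemorrhage. Each should state whether presence excludes or, for microbleeds, what count excludes. Remove the *and no* wording from the exclusion list. The sponsor should reconcile the line with what was intended and confirm the clinical thresholds; none is proposed here.

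The cost is a rewording of one line in Section 4.2. It calls for no extra scans, data or subjects.
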